Bioactive Compounds in Watermelon Modulating Oxidative Stress and Inflammation in Elders

NCT03626168

Study Protocol and Statistical Analysis Plan

February 16, 2016

Protocol

Study participants will be randomized to supplement their diets twice daily with either 100% watermelon juice or an isocaloric placebo for four weeks in a double-blind crossover design. Juice and placebo will be provided in two 12-ounce servings, and participants will be asked to consume one dose in the morning and another in the evening with a meal containing dietary lipid. Based on previous studies^{62,87}, two 12-ounce servings of 100% watermelon juice will provide approximately 1g of L-citrulline and 32 mg of lycopene. Pasteurized watermelon juice for this study will be supplied by Frey Farms (Keenes, IL) from Estrella variety melons. To ensure that all juice contains similar concentrations of the bioactive food compounds of interest, each batch will be tested in the Food and Nutrition Research Laboratory at the University of Alabama for lycopene, citrulline, and arginine content.

Two weeks prior to the intervention, during each intervention arm, and during the washout period, subjects will be asked to consume their typical diet of choice with the exception of foods high in lycopene. A list of lycopene-rich foods such as watermelon and tomato products will be provided, and participants will be asked to limit these foods to two servings per day for the duration of the study. Dietary intake will be closely monitored by 4-day food diaries (three weekdays, one weekend day) submitted during the 2-week run-in period and the 2-week washout period as well as by weekly unannounced 24-hour diet recalls during the treatment period.

Subjects will report to the University of Alabama campus for testing as follows:

Run-In	4-Week Regimen of Juice or Placebo		2-Week Washout	4-Week Regimen of Juice or Placebo	
Days 0-14	Beginning of Week 1	End of Week 4	Weeks 5 & 6	Beginning of Week 7	End of Week 10
4-day food diary	Fasting blood sample	Fasting blood sample	4-day food diary	Fasting blood sample	Fasting blood sample
	Anthropometrics	Anthropometrics		Anthropometrics	Anthropometrics
	FMD	FMD		FMD	FMD
	PWV	PWV		PWV	PWV

Weekly: Weight, Blood Pressure, Adherence

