During weekly visits and phone calls with study personnel, subjects will be queried about adherence to the protocol and acceptability of the beverages. Adherence will be assessed by log forms with check-off boxes for each dose, return of all juice bottles at weekly visits, and random 24-hour diet recalls. Minimal adherence will be defined as 70% of recommended supplementation of two doses per day for four weeks.

Statistical Analysis

A biostatistician from the University of Alabama will be responsible for generating a block randomization with PROC PLAN in SAS (version 9.2). The randomization scheme will balance genotype in Groups 2 and 3 (those who receive genetic information at the beginning of the intervention). Differences between groups will be evaluated by one-way ANOVA with repeated measures with group as the between-subjects factor and time as the within-subjects factor.

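### The plan measures a baseline before each regimen but does not say how either is used; depending on the contrast taken as the juice effect, precision is lost that adjustment could recover

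*Combined protocol and SAP*

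**What the plan says.** The Protocol section has each participant take juice and placebo "for four weeks in a double-blind crossover design", separated by a 2-week washout. Its testing schedule places a fasting blood sample, anthropometrics, FMD and PWV at four visits. Two are baselines, "Beginning of Week 1" and "Beginning of Week 7", and two fall at the end of a regimen (Weeks 4 and 10).

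The Statistical Analysis section gives one sentence on the comparison: "one-way ANOVA with repeated measures with group as the between-subjects factor and time as the within-subjects factor". It names no covariate and no beverage, period or sequence term. It does not list the levels of time or say which contrast estimates juice against placebo. It also does not define group. The only numbered groups are in the sentence before it: "The randomization scheme will balance genotype in Groups 2 and 3 (those who receive genetic information at the beginning of the intervention". That scheme does not appear in the crossover described under Protocol.

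**The concern.** Half of the full test visits are baselines, and the plan gives them no stated role. With only group and time in the model, a natural reading is that juice is judged by change over one regimen against change over the other, which is a group-by-time contrast. Subtracting a noisy baseline from each end value can add more error than it removes. The opposite choice, ignoring the baselines, also loses information when two readings in the same period agree more closely than readings from different periods.

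What is at stake is precision. The interval for juice minus placebo could be wider than the four visits allow, even if washout is complete. Bias is not claimed here.

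**Working it through.** **Inputs.** The four visits come from the testing schedule. The plan states no sample size, power, SD, effect size or correlation, so it has no figure to reproduce. The following are assumptions:
- a common SD σ at all four visits;
- correlation rw between the two readings in one period, and rb between any two readings from different periods;
- no carryover into the Week 7 baseline.

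**Contrasts.** Write b1, e1, b2, e2 for the baseline and end values of periods 1 and 2. Per-person variances in units of σ² are:
- End values only, e1 - e2: 2(1-rb).
- Change against change, (e1-b1) - (e2-b2): 4(1-rw).
- End difference adjusted for baseline difference: 2(1-rb)(1-r²). Here Cov(e1-e2, b1-b2) = 2(rw-rb) and Var(b1-b2) = 2(1-rb), so r = (rw-rb)/(1-rb).

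Since 1-r = (1-rw)/(1-rb), the change-to-adjusted ratio is 4(1-rw) / [2(1-rb)(1-r)(1+r)] = 2/(1+r). The end-only-to-adjusted ratio is 1/(1-r²).

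| rw / rb | r | Change | End only | Adjusted | Change ÷ adjusted | End only ÷ adjusted |
|---|---|---|---|---|---|---|
| 0.6 / 0.6 | 0 | 1.60 | 0.80 | 0.80 | 2.00 | 1.00 |
| 0.7 / 0.6 | 0.25 | 1.20 | 0.80 | 0.75 | 1.60 | 1.07 |
| 0.8 / 0.6 | 0.50 | 0.80 | 0.80 | 0.60 | 1.33 | 1.33 |
| 0.9 / 0.6 | 0.75 | 0.40 | 0.80 | 0.35 | 1.14 | 2.29 |
| 0.5 / 0.6 | -0.25 | 2.00 | 0.80 | 0.75 | 2.67 | 1.07 |

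A simulation with 20 people per sequence and 8,000 runs gave change-to-adjusted ratios of 1.98 at 0.5/0.5 (formula 2.00) and 1.24 at 0.8/0.5 (formula 1.25).

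**In terms of power.** Suppose the adjusted analysis had 80% power at two-sided 0.05 (also assumed). At variance ratio R, power is Φ[(1.96+0.84)/√R - 1.96]. That is 51% at R = 2.00, 68% at 1.33 and 75% at 1.14.

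**Does entering baselines as levels of time cause the loss?** Take a model with participant, four-level time and a juice indicator. Its juice estimate weights the visits (0, +, 0, -) in the juice-first sequence and the reverse in the other. Both baselines get weight zero, so this is the end-only comparison, with no loss at r = 0. The loss comes from the contrast chosen.

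**If group means sequence.** Both sequences receive juice once, so the group main effect contains no juice effect. With a true effect of 0.5, its simulated mean was about 0.

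**How the adjustment must be coded.** The baseline difference is one number per person, the same on both of that person's rows. With complete data, beverage is estimated within person, so a person-constant main effect cannot move it. At rw/rb = 0.8/0.6 with 20 per sequence, theory gives an SE of √(0.80/20 + 0.80/20)/2 = 0.141 without adjustment and √(0.60/20 + 0.60/20)/2 = 0.122 with it. In 300 simulated runs the mean SE was 0.1398 both without the covariate and with it as a main effect, and 0.1227 once it was crossed with period.

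**The case against.** A reader might infer that the plan enters the two baselines as extra levels of time and thereby doubles the error variance of the juice effect. The documents do not support this. They never list the levels of time, so that use of the baselines is an inference. Extra time levels do no harm by themselves, as the (0, +, 0, -) weights show. Doubling is the r = 0 case of a range, and no correlation is given from which to place this trial within it.

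A second objection is that the model defines no juice effect at all, so there is no error variance to inflate. This stands as a prior gap: without a beverage, period or sequence term, the efficiency question is conditional on a reading of the plan. It does not remove the point. The readings that use the named factors either give a less precise contrast or fail to isolate juice, and the model that closes the gap is also where the baselines need a role.

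Third, change-score analysis is a valid method and only precision is at issue. That is correct, and it limits the seriousness of the point. When r is high (0.9/0.6 in the table), the change contrast comes within 14% of the adjusted variance, and ignoring the baselines is the worse choice.

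**Conclusion.** The point holds in a conditional form. The plan collects two period baselines, makes no covariate use of them, and names no term for beverage, period or sequence. Relative to adjustment, a change contrast has 2/(1+r) times the variance: between 1.14 and 2.00 for r from 0.75 down to 0, and above 2 if r is negative. An end-only comparison has 1/(1-r²) times the variance: 1.00 at r = 0, 1.33 at r = 0.5 and 2.29 at r = 0.75. In large samples adjustment is never less precise than either.

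These sizes rest on the assumed correlation pattern, equal SDs and no carryover at Week 7. The loss for this trial cannot be fixed from the documents. The change is worth making because the data are already being collected.

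**What to change.** Replace the model in the Statistical Analysis section with a crossover analysis of the Week 4 and Week 10 end values. Use beverage, period and sequence as fixed effects and participant as random. For each outcome, include the baseline difference (Week 1 minus Week 7) of the same measure, crossed with period.

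Equivalently, regress each person's end-value difference (Week 4 minus Week 10) on sequence and the baseline difference. With sequence coded +1 for juice first and -1 for placebo first, its coefficient is juice minus placebo, and the intercept carries the period effect. The SAP should state the crossing with period explicitly, because the main effect alone leaves the beverage estimate and its SE unchanged.

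The cost is one SAP sentence and one degree of freedom per outcome, with no new data. If r is near 0 there is a slight small-sample loss: with 20 per sequence at rw = rb = 0.5, the simulated variance was 0.02534 adjusted against 0.02472 end-only, a ratio of 1.025.
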